[†]Adverse events are product-use emergent

Adverse events occurred between discharge and end of study for the subject

Program: /AAXXXX/ECR/sas_prg/stsas/tab programname.sas DDMMYYYY HH:MM Status: DRAFT (Page X of Y)

Philip Morris Products S.A.
P4M3 Gen 2.0, P4-PK-04-US

████████████████████ Statistical Analysis Plan Number CA34617

Table 15.2.3.1.3 will have the following format:

Table 15.2.3.1.3 Summary of Adverse Events by System Organ Class, Preferred Term, Product, and Relationship to Study Product Including Expectedness (Safety Population)

System Organ Class Preferred Term	Study Product							Safety Follow-up [#] N=XX	
	P4M3 Gen 2.0								
	CA35 Test [†] N=XX n (%) Events	CA35 [†] N=XX n (%) Events	CM35 [†] N=XX n (%) Events	Cigarettes [†] N=XX n (%) Events	Overall [†] N=XX n (%) Events	Overall [†] N=XX n (%) Events	Overall [†] N=XX n (%) Events		
Any Adverse events	X (XX%) XX	X (XX%) XX	X (XX%) XX	X (XX%) XX	X (XX%) XX	X (XX%) XX	X (XX%) XX		
Related to IP	X (XX%) XX	X (XX%) XX	X (XX%) XX	X (XX%) XX	X (XX%) XX	X (XX%) XX	X (XX%) XX		
Expected	X (XX%) XX	X (XX%) XX	X (XX%) XX	X (XX%) XX	X (XX%) XX	X (XX%) XX	X (XX%) XX		
Unexpected	X (XX%) XX	X (XX%) XX	X (XX%) XX	X (XX%) XX	X (XX%) XX	X (XX%) XX	X (XX%) XX		
SOC 1	X (XX%) XX	X (XX%) XX	X (XX%) XX	X (XX%) XX	X (XX%) XX	X (XX%) XX	X (XX%) XX		
Preferred term 1	X (XX%) XX	X (XX%) XX	X (XX%) XX	X (XX%) XX	X (XX%) XX	X (XX%) XX	X (XX%) XX		
Related to IP	X (XX%) XX	X (XX%) XX	X (XX%) XX	X (XX%) XX	X (XX%) XX	X (XX%) XX	X (XX%) XX		
Expected	X (XX%) XX	X (XX%) XX	X (XX%) XX	X (XX%) XX	X (XX%) XX	X (XX%) XX	X (XX%) XX		
Unexpected	X (XX%) XX	X (XX%) XX	X (XX%) XX	X (XX%) XX	X (XX%) XX	X (XX%) XX	X (XX%) XX		
Unrelated to IP	X (XX%) XX	X (XX%) XX	X (XX%) XX	X (XX%) XX	X (XX%) XX	X (XX%) XX	X (XX%) XX		

CA35 = P4M3 Gen 2.0 Classic Auburn

CM35 = P4M3 Gen 2.0 Classic Menthol

Safety Population = All subjects who underwent screening, give informed consent, have at least one exposure to P4M3 Gen 2.0 and have at least one safety assessment

*Adverse events are classified according to MedDRA Version 24.0

†Adverse events are product-use emergent

Adverse events occurred between discharge and end of study for the subject

Program: /AAXXXXXX/ECR/sas_prg/stsas/tab programname.sas DDMMYY YYYY HH:MM Status: DRAFT (Page X of Y)

Philip Morris Products S.A.
P4M3 Gen 2.0, P4-PK-04-US

████████ Statistical Analysis Plan Number CA34617

Table 15.2.3.1.4 will have the following format:

Table 15.2.3.1.4 Summary of Adverse Events by System Organ Class, Preferred Term, Product, and Relationship to Study Procedure (Safety Population)

System Organ Class Preferred Term	Study Product							Safety Follow-up [#] N=XX	
	P4M3 Gen 2.0								
	CA35 Test [†] N=XX n (%) Events	CA35 [†] N=XX n (%) Events	CM35 [†] N=XX n (%) Events	Cigarettes [†] N=XX n (%) Events	Overall [†] N=XX n (%) Events				
Adverse events (AE) related to study procedures	X (XX%) XX	X (XX%) XX	X (XX%) XX	X (XX%) XX	X (XX%) XX	X (XX%) XX	X (XX%) XX		
SOC1	X (XX%) XX	X (XX%) XX	X (XX%) XX	X (XX%) XX	X (XX%) XX	X (XX%) XX	X (XX%) XX		
Preferred term 1	X (XX%) XX	X (XX%) XX	X (XX%) XX	X (XX%) XX	X (XX%) XX	X (XX%) XX	X (XX%) XX		
Preferred term 2	X (XX%) XX	X (XX%) XX	X (XX%) XX	X (XX%) XX	X (XX%) XX	X (XX%) XX	X (XX%) XX		
Preferred term n	X (XX%) XX	X (XX%) XX	X (XX%) XX	X (XX%) XX	X (XX%) XX	X (XX%) XX	X (XX%) XX		
SOC2	X (XX%) XX	X (XX%) XX	X (XX%) XX	X (XX%) XX	X (XX%) XX	X (XX%) XX	X (XX%) XX		
Preferred term 1	X (XX%) XX	X (XX%) XX	X (XX%) XX	X (XX%) XX	X (XX%) XX	X (XX%) XX	X (XX%) XX		
Preferred term 2	X (XX%) XX	X (XX%) XX	X (XX%) XX	X (XX%) XX	X (XX%) XX	X (XX%) XX	X (XX%) XX		
Preferred term n	X (XX%) XX	X (XX%) XX	X (XX%) XX	X (XX%) XX	X (XX%) XX	X (XX%) XX	X (XX%) XX		

CA35 = P4M3 Gen 2.0 Classic Auburn

CM35 = P4M3 Gen 2.0 Classic Menthol

Safety Population = All subjects who underwent screening, give informed consent, have at least one exposure to P4M3 Gen 2.0 and have at least one safety assessment

*Adverse events are classified according to MedDRA Version 24.0

[†]Adverse events are product-use emergent

Adverse events occurred between discharge and end of study for the subject

Program: /AAXXXXXX/ECR/sas_prg/stsas/tab programname.sas DDMMYY YYYY HH:MM Status: DRAFT (Page X of Y)

Philip Morris Products S.A.

P4M3 Gen 2.0, P4-PK-04-US

[REDACTED] Statistical Analysis Plan Number CA34617

Table 15.2.3.1.5 will have the following format:

Table 15.2.3.1.5 Summary of Adverse Events by System Organ Class, Preferred Term, Product, and Severity (Safety Population)

System Organ Class Preferred Term	Study Product							Safety Follow-up [#] N=XX	
	P4M3 Gen 2.0								
	CA35 Test [†] N=XX n (%) Events	CA35 [†] N=XX n (%) Events	CM35 [†] N=XX n (%) Events	Cigarettes [†] N=XX n (%) Events	Overall [†] N=XX n (%) Events				
Adverse Events	X (XX%) XX	X (XX%) XX	X (XX%) XX	X (XX%) XX	X (XX%) XX	X (XX%) XX	X (XX%) XX		
Mild	X (XX%) XX	X (XX%) XX	X (XX%) XX	X (XX%) XX	X (XX%) XX	X (XX%) XX	X (XX%) XX		
Moderate	X (XX%) XX	X (XX%) XX	X (XX%) XX	X (XX%) XX	X (XX%) XX	X (XX%) XX	X (XX%) XX		
Severe	X (XX%) XX	X (XX%) XX	X (XX%) XX	X (XX%) XX	X (XX%) XX	X (XX%) XX	X (XX%) XX		
SOC1	X (XX%) XX	X (XX%) XX	X (XX%) XX	X (XX%) XX	X (XX%) XX	X (XX%) XX	X (XX%) XX		
Preferred term 1	X (XX%) XX	X (XX%) XX	X (XX%) XX	X (XX%) XX	X (XX%) XX	X (XX%) XX	X (XX%) XX		
Mild	X (XX%) XX	X (XX%) XX	X (XX%) XX	X (XX%) XX	X (XX%) XX	X (XX%) XX	X (XX%) XX		
Moderate	X (XX%) XX	X (XX%) XX	X (XX%) XX	X (XX%) XX	X (XX%) XX	X (XX%) XX	X (XX%) XX		
Severe	X (XX%) XX	X (XX%) XX	X (XX%) XX	X (XX%) XX	X (XX%) XX	X (XX%) XX	X (XX%) XX		
Preferred term 2	X (XX%) XX	X (XX%) XX	X (XX%) XX	X (XX%) XX	X (XX%) XX	X (XX%) XX	X (XX%) XX		
Mild	X (XX%) XX	X (XX%) XX	X (XX%) XX	X (XX%) XX	X (XX%) XX	X (XX%) XX	X (XX%) XX		
Moderate	X (XX%) XX	X (XX%) XX	X (XX%) XX	X (XX%) XX	X (XX%) XX	X (XX%) XX	X (XX%) XX		
Severe	X (XX%) XX	X (XX%) XX	X (XX%) XX	X (XX%) XX	X (XX%) XX	X (XX%) XX	X (XX%) XX		

CA35 = P4M3 Gen 2.0 Classic Auburn

CM35 = P4M3 Gen 2.0 Classic Menthol

Safety Population = All subjects who underwent screening, give informed consent, have at least one exposure to P4M3 Gen 2.0 and have at least one safety assessment

*Adverse events are classified according to MedDRA Version 24.0

†Adverse events are product-use emergent

Adverse events occurred between discharge and end of study for the subject

Program: /AAXXXX/ECR/sas_prg/stsas/tab programname.sas DDMMYYYY HH:MM Status: DRAFT (Page X of Y)

Philip Morris Products S.A.
P4M3 Gen 2.0, P4-PK-04-US

████████ Statistical Analysis Plan Number CA34617

Table 15.2.3.1.6 will have the following format:

Table 15.2.3.1.6 Summary of Adverse Events Leading to Product Discontinuation by System Organ Class, Preferred Term (Safety Population)

System Organ Class Preferred Term	Study Product				
	P4M3 Gen 2.0				
	CA35 Test [†] N=XX n (%) Events	CA35 [†] N=XX n (%) Events	CM35 [†] N=XX n (%) Events	Cigarettes [†] N=XX n (%) Events	Overall [†] N=XX n (%) Events
Any Adverse Events leading to product discontinuation	X (XX%) XX	X (XX%) XX	X (XX%) XX	X (XX%) XX	X (XX%) XX
SOC1	X (XX%) XX	X (XX%) XX	X (XX%) XX	X (XX%) XX	X (XX%) XX
Preferred term 1	X (XX%) XX	X (XX%) XX	X (XX%) XX	X (XX%) XX	X (XX%) XX
Preferred term 2	X (XX%) XX	X (XX%) XX	X (XX%) XX	X (XX%) XX	X (XX%) XX
Preferred term n	X (XX%) XX	X (XX%) XX	X (XX%) XX	X (XX%) XX	X (XX%) XX

CA35 = P4M3 Gen 2.0 Classic Auburn

CM35 = P4M3 Gen 2.0 Classic Menthol

Safety Population = All subjects who underwent screening, give informed consent, have at least one exposure to P4M3 Gen 2.0 and have at least one safety assessment

*Adverse events are classified according to MedDRA Version 24.0

[†]Adverse events are product-use emergent

Program: /AAXXXX/ECR/sas_prg/stsas/tab prgname.sas DDMMYYYY HH:MM Status: DRAFT (Page X of Y)

Programmer note; If there is no AE leading for product discontinuation, a note will be added to the table as “There were no AEs leading to product discontinuation during the study”.

Philip Morris Products S.A.
P4M3 Gen 2.0, P4-PK-04-US

████████ Statistical Analysis Plan Number CA34617

Table 15.2.3.1.7 will have the following format:

Table 15.2.3.1.7 Summary of Adverse Events Leading to Study Discontinuation by System Organ Class, Preferred Term, and Product (Safety Population)

System Organ Class Preferred Term	Study Product				
	P4M3 Gen 2.0				
	CA35 Test [†] N=XX n (%) Events	CA35 [†] N=XX n (%) Events	CM35 [†] N=XX n (%) Events	Cigarettes [†] N=XX n (%) Events	Overall [†] N=XX n (%) Events
Any Adverse Events leading to study discontinuation	X (XX%) XX	X (XX%) XX	X (XX%) XX	X (XX%) XX	X (XX%) XX
SOC1	X (XX%) XX	X (XX%) XX	X (XX%) XX	X (XX%) XX	X (XX%) XX
Preferred term 1	X (XX%) XX	X (XX%) XX	X (XX%) XX	X (XX%) XX	X (XX%) XX
Preferred term 2	X (XX%) XX	X (XX%) XX	X (XX%) XX	X (XX%) XX	X (XX%) XX
Preferred term n	X (XX%) XX	X (XX%) XX	X (XX%) XX	X (XX%) XX	X (XX%) XX

CA35 = P4M3 Gen 2.0 Classic Auburn

CM35 = P4M3 Gen 2.0 Classic Menthol

Safety Population = All subjects who underwent screening, give informed consent, have at least one exposure to P4M3 Gen 2.0 and have at least one safety assessment

*Adverse events are classified according to MedDRA Version 24.0

†Adverse events are product-use emergent

Program: /AAXXXX/ECR/sas_prg/stsas/tab prgname.sas DDMMYYYY HH:MM Status: DRAFT (Page X of Y)

Programmer note: If there is no AE leading for study discontinuation, a note will be added to the table as “There were no AEs leading to study discontinuation during the study”.

Philip Morris Products S.A.
P4M3 Gen 2.0, P4-PK-04-US

████████████████████ Statistical Analysis Plan Number CA34617

Table 15.2.3.1.8 will have the following format:

Table 15.2.3.1.8 Summary of Adverse Events With Action Taken Related to the Product by System Organ Class, Preferred Term, and Product (Safety Population)

System Organ Class Preferred Term	Study Product				
	P4M3 Gen 2.0				
	CA35 Test [†] N=XX n (%) Events	CA35 [†] N=XX n (%) Events	CM35 [†] N=XX n (%) Events	Cigarettes [†] N=XX n (%) Events	Overall [†] N=XX n (%) Events
Adverse Events	X (XX%) XX	X (XX%) XX	X (XX%) XX	X (XX%) XX	X (XX%) XX
No action taken	X (XX%) XX	X (XX%) XX	X (XX%) XX	X (XX%) XX	X (XX%) XX
Action taken for product	X (XX%) XX	X (XX%) XX	X (XX%) XX	X (XX%) XX	X (XX%) XX
SOC1	X (XX%) XX	X (XX%) XX	X (XX%) XX	X (XX%) XX	X (XX%) XX
No action taken	X (XX%) XX	X (XX%) XX	X (XX%) XX	X (XX%) XX	X (XX%) XX
Action taken for product	X (XX%) XX	X (XX%) XX	X (XX%) XX	X (XX%) XX	X (XX%) XX
Preferred term 1	X (XX%) XX	X (XX%) XX	X (XX%) XX	X (XX%) XX	X (XX%) XX
No action taken	X (XX%) XX	X (XX%) XX	X (XX%) XX	X (XX%) XX	X (XX%) XX
Action taken for product	X (XX%) XX	X (XX%) XX	X (XX%) XX	X (XX%) XX	X (XX%) XX
Preferred term 2	X (XX%) XX	X (XX%) XX	X (XX%) XX	X (XX%) XX	X (XX%) XX
No action taken	X (XX%) XX	X (XX%) XX	X (XX%) XX	X (XX%) XX	X (XX%) XX
Action taken for product	X (XX%) XX	X (XX%) XX	X (XX%) XX	X (XX%) XX	X (XX%) XX

CA35 = P4M3 Gen 2.0 Classic Auburn

CM35 = P4M3 Gen 2.0 Classic Menthol

Safety Population = All subjects who underwent screening, give informed consent, have at least one exposure to P4M3 Gen 2.0 and have at least one safety assessment

*Adverse events are classified according to MedDRA Version 24.0

†Adverse events are product-use emergent

Program: /AAXXXXXX/ECR/sas_prg/stsas/tab prgname.sas DDMMYYYY HH:MM Status: DRAFT (Page X of Y)

Philip Morris Products S.A.

P4M3 Gen 2.0, P4-PK-04-US

[REDACTED] Statistical Analysis Plan Number CA34617

Table 15.2.3.1.9 will have the following format:

Table 15.2.3.1.9 Summary of Serious Adverse Events (Safety Population)

	Study Product							Safety Follow-up [#]	
	CA35 Test [†]		CA35 [†]		CM35 [†]		Cigarettes [†]		
	N=XX	n (%) Events	N=XX	n (%) Events	N=XX	n (%) Events			
Serious Adverse Events									
Death	X (XX%) XX	X (XX%) XX	X (XX%) XX	X (XX%) XX	X (XX%) XX	X (XX%) XX	X (XX%) XX	X (XX%) XX	
Life threatening	X (XX%) XX	X (XX%) XX	X (XX%) XX	X (XX%) XX	X (XX%) XX	X (XX%) XX	X (XX%) XX	X (XX%) XX	
Hospitalization	X (XX%) XX	X (XX%) XX	X (XX%) XX	X (XX%) XX	X (XX%) XX	X (XX%) XX	X (XX%) XX	X (XX%) XX	
Disability	X (XX%) XX	X (XX%) XX	X (XX%) XX	X (XX%) XX	X (XX%) XX	X (XX%) XX	X (XX%) XX	X (XX%) XX	
Congenital anomaly	X (XX%) XX	X (XX%) XX	X (XX%) XX	X (XX%) XX	X (XX%) XX	X (XX%) XX	X (XX%) XX	X (XX%) XX	
Important medical event	X (XX%) XX	X (XX%) XX	X (XX%) XX	X (XX%) XX	X (XX%) XX	X (XX%) XX	X (XX%) XX	X (XX%) XX	
Severity									
Mild	X (XX%) XX	X (XX%) XX	X (XX%) XX	X (XX%) XX	X (XX%) XX	X (XX%) XX	X (XX%) XX	X (XX%) XX	
Moderate	X (XX%) XX	X (XX%) XX	X (XX%) XX	X (XX%) XX	X (XX%) XX	X (XX%) XX	X (XX%) XX	X (XX%) XX	
Severe	X (XX%) XX	X (XX%) XX	X (XX%) XX	X (XX%) XX	X (XX%) XX	X (XX%) XX	X (XX%) XX	X (XX%) XX	
Related to study product									
Related	X (XX%) XX	X (XX%) XX	X (XX%) XX	X (XX%) XX	X (XX%) XX	X (XX%) XX	X (XX%) XX	X (XX%) XX	
Unrelated	X (XX%) XX	X (XX%) XX	X (XX%) XX	X (XX%) XX	X (XX%) XX	X (XX%) XX	X (XX%) XX	X (XX%) XX	
Related to study Procedure									
Related	X (XX%) XX	X (XX%) XX	X (XX%) XX	X (XX%) XX	X (XX%) XX	X (XX%) XX	X (XX%) XX	X (XX%) XX	
Unrelated	X (XX%) XX	X (XX%) XX	X (XX%) XX	X (XX%) XX	X (XX%) XX	X (XX%) XX	X (XX%) XX	X (XX%) XX	

CA35 = P4M3 Gen 2.0 Classic Auburn

CM35 = P4M3 Gen 2.0 Classic Menthol

Safety Population = All subjects who underwent screening, give informed consent, have at least one exposure to P4M3 Gen 2.0 and have at least one safety assessment

*Adverse events are classified according to MedDRA Version 24.0

[†]Adverse events are product-use emergent

Adverse events occurred between discharge and end of study for the subject

Program: /AAXXXX/ECR/sas_prg/stsas/tab prgname.sas DDMMYYYY HH:MM Status: DRAFT (Page X of Y)

Programmer note: If there are no SAEs, a note will be added to the table as “No serious adverse events were reported during the study”.

Philip Morris Products S.A.
P4M3 Gen 2.0, P4-PK-04-US

████████████████████ Statistical Analysis Plan Number CA34617

Table 15.2.3.1.10 will have the following format:

Table 15.2.3.1.10 Summary of Serious Adverse Events by System Organ Class, Preferred Term, and Product (Safety Population)

System Organ Class Preferred Term	Study Product							Safety Follow-up [#] N=XX	
	P4M3 Gen 2.0								
	CA35 Test [†] N=XX n (%) Events	CA35 [†] N=XX n (%) Events	CM35 [†] N=XX n (%) Events	Cigarettes [†] N=XX n (%) Events	Overall [†] N=XX n (%) Events				
Any Serious Adverse Events	X (XX%) XX	X (XX%) XX	X (XX%) XX	X (XX%) XX	X (XX%) XX	X (XX%) XX	X (XX%) XX		
SOC1	X (XX%) XX	X (XX%) XX	X (XX%) XX	X (XX%) XX	X (XX%) XX	X (XX%) XX	X (XX%) XX		
Preferred term 1	X (XX%) XX	X (XX%) XX	X (XX%) XX	X (XX%) XX	X (XX%) XX	X (XX%) XX	X (XX%) XX		
Preferred term 2	X (XX%) XX	X (XX%) XX	X (XX%) XX	X (XX%) XX	X (XX%) XX	X (XX%) XX	X (XX%) XX		
Preferred term n	X (XX%) XX	X (XX%) XX	X (XX%) XX	X (XX%) XX	X (XX%) XX	X (XX%) XX	X (XX%) XX		
SOC2	X (XX%) XX	X (XX%) XX	X (XX%) XX	X (XX%) XX	X (XX%) XX	X (XX%) XX	X (XX%) XX		
Preferred term 1	X (XX%) XX	X (XX%) XX	X (XX%) XX	X (XX%) XX	X (XX%) XX	X (XX%) XX	X (XX%) XX		
Preferred term 2	X (XX%) XX	X (XX%) XX	X (XX%) XX	X (XX%) XX	X (XX%) XX	X (XX%) XX	X (XX%) XX		
Preferred term n	X (XX%) XX	X (XX%) XX	X (XX%) XX	X (XX%) XX	X (XX%) XX	X (XX%) XX	X (XX%) XX		

CA35 = P4M3 Gen 2.0 Classic Auburn

CM35 = P4M3 Gen 2.0 Classic Menthol

Safety Population = All subjects who underwent screening, give informed consent, have at least one exposure to P4M3 Gen 2.0 and have at least one safety assessment

*Adverse events are classified according to MedDRA Version 24.0

[†]Adverse events are product-use emergent

Adverse events occurred between discharge and end of study for the subject

Program: /AAXXXX/ECR/sas_prg/stsas/tab programname.sas DDMMYYYY HH:MM Status: DRAFT (Page X of Y)

Programmer note: If there are no SAEs, a note will be added to the table as “No serious adverse events were reported during the study”.

Philip Morris Products S.A.
P4M3 Gen 2.0, P4-PK-04-US

████████ Statistical Analysis Plan Number CA34617

Table 15.2.3.1.11 will have the following format:

Table 15.2.3.1.11 Summary of P4M3 Gen 2.0 Product Events and Malfunction/Misuse (Safety Population)

Product Event	P4M3 Gen 2.0		
	CA35	CM35	Overall
Number of Subjects Who Received Study Product	XX (100%)	XX (100%)	XX (100%)
Number of Subjects Reported Product Event	X (X%)	X (X%)	X (X%)
Break	X (X%)	X (X%)	X (X%)
Major	X (X%)	X (X%)	X (X%)
Minor	X (X%)	X (X%)	X (X%)
Fluid Leak	X (X%)	X (X%)	X (X%)
Major	X (X%)	X (X%)	X (X%)
Minor	X (X%)	X (X%)	X (X%)
Intermittent Loss of Power	X (X%)	X (X%)	X (X%)
Major	X (X%)	X (X%)	X (X%)
Minor	X (X%)	X (X%)	X (X%)
Power Problem	X (X%)	X (X%)	X (X%)
Major	X (X%)	X (X%)	X (X%)
Minor	X (X%)	X (X%)	X (X%)
Premature Indicator Activation	X (X%)	X (X%)	X (X%)
Major	X (X%)	X (X%)	X (X%)
Minor	X (X%)	X (X%)	X (X%)
Other	X (X%)	X (X%)	X (X%)
Major	X (X%)	X (X%)	X (X%)
Minor	X (X%)	X (X%)	X (X%)
Product events leading to AEs	X (X%)	X (X%)	X (X%)
Misuse	X (X%)	X (X%)	X (X%)

CA35 = P4M3 Gen 2.0 Classic Auburn

CM35 = P4M3 Gen 2.0 Classic Menthol

Safety Population = All subjects who underwent screening, give informed consent, have at least one exposure to P4M3 Gen 2.0 and have at least one safety assessment

Program: /AAXXXX/ECR/sas_prg/stsas/tab prgname.sas DDMMYY YYYY HH:MM Status: DRAFT (Page X of Y)

Philip Morris Products S.A.

P4M3 Gen 2.0, P4-PK-04-US

[REDACTED] Statistical Analysis Plan Number CA34617

Tables 15.2.3.2.2 and 15.2.3.2.3 will resemble Table 15.2.3.2.1

Table 15.2.3.2.1 Summary and Change from Baseline of Clinical Chemistry Parameters (Safety Population)

Laboratory Test (units)	Normal Range	Statistic	Original Value			Change from Baseline	
			Screen	Admission Day -1	Discharge Day 3	Discharge Day 3	
Testname (unit)	< - >#	n	X	X	X		X
		Mean	X.X*	X.X	X.X		X.X
		SD	X.XX	X.XX	X.XX		X.XX
		CV%	X.X	X.X	X.X		X.X
		SEM	X.XX	XX.X	XX.X		XX.X
		Minimum	XX	XX	XX		XX
		Q1	X.X	X.X	X.X		X.X
		Median	X.X	X.X	X.X		X.X
		Q3	X.X	X.X	X.X		X.X
		Maximum	XX	XX	XX		XX
		95% CI	XX-XX	XX-XX	XX-XX		XX-XX
Testname (unit)	< - >	n	X	X	X		X
		Mean	X.X	X.X	X.X		X.X
		SD	X.XX	X.XX	X.XX		X.XX
		CV%	X.X	X.X	X.X		X.X
		SEM	X.XX	XX.X	XX.X		XX.X
		Minimum	XX	XX	XX		XX
		Q3	X.X	X.X	X.X		X.X
		Median	X.X	X.X	X.X		X.X
		Q3	X.X	X.X	X.X		X.X
		Maximum	XX	XX	XX		XX
		95% CI	XX-XX	XX-XX	XX-XX		XX-XX

= Lowest of the lower ranges and highest of the higher ranges are used. Refer to Listing 16.1.9.1 for the breakdown.

* Above Normal Range, ^ Below Normal Range

Baseline is the result closest and prior to the first product administration (Admission Day -1).

SD = Standard deviation, CV% = Coefficient of variance, SEM = Standard error of mean, Q1 = 1st quartile, Q3 = 3rd quartile, CI = Confidence interval

Safety Population = All subjects who underwent screening, give informed consent, have at least one exposure to P4M3 Gen 2.0, and have at least one safety assessment

Program: /CAXXXX/ECR/sas_prg/stsas/tab programname.sas DDMMYYYY HH:MM Status:DRAFT (Page X of Y)

Programmer note: Similar for remaining laboratory tests.

Philip Morris Products S.A.
P4M3 Gen 2.0, P4-PK-04-US

████████ Statistical Analysis Plan Number CA34617

Table 15.2.3.3.1 will have the following format.

Table 15.2.3.3.1 Summary of Vital Signs and Change from Baseline (Safety Population)

Vital signs (units)	Time Point	Statistic	Original Value	Change from Baseline
Testname (unit)	Screen	n	X	
		Mean	XX	
		SD	XXX	
		CV%	XX	
		SEM	XX	
		Minimum	XX	
		Q1	XX	
		Median	XX	
		Q3	XX	
		Maximum	XX	
	Day -1	95% CI	XX-XX	
		n	X	
		Mean	XX	
		SD	XXX	
		CV%	XX	
		SEM	XX	
		Minimum	XX	
		Q1	XX	
		Median	XX	
		Q3	XX	
Overall Results	Screen	Maximum	XX	
		95% CI	XX-XX	
		Normal	X(XX%)	
		Abnormal NCS	X(XX%)	
		Abnormal CS	X(XX%)	

Baseline is the result closest and prior to the first product administration (Day 1).

SD = Standard deviation, CV% = Coefficient of variance, SEM = Standard error of mean, Q1 = 1st quartile, Q3 = 3rd quartile, CI = Confidence interval

NCS = Not clinically significant, CS = Clinically significant

Safety Population = All subjects who underwent screening, give informed consent, have at least one exposure to P4M3 Gen 2.0 and have at least one safety assessment

Program: /CAXXXX/ECR/sas_prg/stsas/tab programname.sas DDMMYY HH:MM Status: DRAFT (Page X of Y)

Programmer note: Similar for remaining vital signs measurements. Change from baseline will be presented for the time points after Day 1. Overall results will be presented as frequency count and percentage by time point.

Philip Morris Products S.A.
P4M3 Gen 2.0, P4-PK-04-US

████████ Statistical Analysis Plan Number CA34617

Table 15.2.3.4.1 will have the following format.

Table 15.2.3.4.1 Summary of 12-Lead Electrocardiogram and Change from Baseline (Safety Population)

Parameter (unit)	Statistic	Screen	Original Value		Change from Baseline
			Admission Day -1	Discharge Day 3	Discharge Day 3
Testname (unit)	n	X	X	X	X
	Mean	X.X	X.X	X.X	XX
	SD	X.XX	X.XX	X.XX	X.XX
	CV%	X.X	X.X	X.X	X.X
	SEM	X.XX	X.XX	X.XX	X.XX
	Minimum	XX	XX	XX	XX
	Q1	X.X	X.X	X.X	X.X
	Median	X.X	X.X	X.X	X.X
	Q3	X.X	X.X	X.X	X.X
	Maximum	XX	XX	XX	XX
	95% CI	XX-XX	XX-XX	XX-XX	XX-XX
Overall Interpretation	Normal	X(XX%)	X(XX%)	X(XX%)	
	Abnormal NCS	X(XX%)	X(XX%)	X(XX%)	
	Abnormal CS	X(XX%)	X(XX%)	X(XX%)	

Baseline is the result closest and prior to the first product administration (Admission Day -1).

SD = Standard deviation, CV% = Coefficient of variance, SEM = Standard error of mean, Q1 = 1st quartile, Q3 = 3rd quartile, CI = Confidence interval

NCS = Not clinically significant, CS = Clinically significant

Safety Population = All subjects who underwent screening, give informed consent, have at least one exposure to P4M3 Gen 2.0 and have at least one safety assessment

Program: /CAXXXX/ECR/sas_prg/stsas/tab programname.sas DDMMYY HH:MM Status: DRAFT (Page X of Y)

Programmer note: Similar for remaining ECG parameters.

Philip Morris Products S.A.
P4M3 Gen 2.0, P4-PK-04-US

████████ Statistical Analysis Plan Number CA34617

Table 15.2.3.5.1 will have the following format:

Table 15.2.3.5.1 Summary of Concomitant Medication by Anatomical Therapeutic Classes (ATC) 1 and 2 (Safety Population)

Concomitant Medication*	Product			
	CA35	CM35	Cigarettes	Overall
Number of Subjects Who Received Study Product	XX (100%)	XX (100%)	XX (100%)	XX (100%)
Number of Subjects Used Concomitant Medication	X (XX%)	X (XX%)	X (XX%)	X (XX%)
ATC1	X (X%)	X (X%)	X (X%)	X (X%)
ATC2	X (X%)	X (X%)	X (X%)	X (X%)

CA35 = P4M3 Gen 2.0 Classic Auburn

CM35 = P4M3 Gen 2.0 Classic Menthol

Safety Population = All subjects who underwent screening, give informed consent, have at least one exposure to P4M3 Gen 2.0 and have at least one safety assessment

* Concomitant medication is classified according to WHO DD Version 01MAR2021.

Medication taken prior to the first product use and after discharge from CRU are not included in the analysis.

Program: /AAXXXX/ECR/sas_prg/stsas/tab prgrname.sas DDMMYY HH:MM Status: DRAFT (Page X of Y)

Philip Morris Products S.A.
P4M3 Gen 2.0, P4-PK-04-US

████████ Statistical Analysis Plan Number CA34617

Table 15.2.3.6.1 will have the following format.

Table 15.2.3.6.1 Summary of Spirometry and Change from Baseline (Safety Population)

Parameter (unit)	Statistic	Original Value		Change from Baseline	
		Screening	Admission (Day -1)	Discharge (Day 3)	Discharge (Day 3)
Testname (unit)	n	X	X	X	X
	Mean	X.X	X.X	X.X	X.X
	SD	X.XX	X.XX	X.XX	X.XX
	CV%	X.X	X.X	X.X	X.X
	SEM	X.XX	X.XX	X.XX	X.XX
	Minimum	XX	XX	XX	XX
	Q1	XX	XX	XX	XX
	Median	X.X	X.X	X.X	X.X
	Q3	XX	XX	XX	XX
	Maximum	XX	XX	XX	XX
Overall Result	95% CI	XX-XX	XX-XX	XX-XX	XX-XX
	Normal	X (XX%)	X (XX%)	X (XX%)	X (XX%)
	Abnormal NCS	X(XX%)	X(XX%)	X(XX%)	X(XX%)
	Abnormal CS	X(XX%)	X(XX%)	X(XX%)	X(XX%)

Baseline is the result closest and prior to the first product administration (Day -1).

SD = Standard deviation, CV% = Coefficient of variance, SEM = Standard error of mean, Q1 = 1st quartile, Q3 = 3rd quartile, CI = Confidence interval

NCS = Not clinically significant, CS = Clinically significant

Safety Population = All subjects who underwent screening, give informed consent, have at least one exposure to P4M3 Gen 2.0 and have at least one safety assessment

Program: /CAXXXXX/ECR/sas_prg/stsas/tab programname.sas DDMMYY YYYY HH:MM Status: DRAFT (Page X of Y)

Programmer note: Similar for remaining Spirometry parameters.

Philip Morris Products S.A.
P4M3 Gen 2.0, P4-PK-04-US
[REDACTED] Statistical Analysis Plan Number CA34617

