7.3 Inferential Analysis

An analysis of covariance (ANCOVA) will be conducted by product use. The PK parameters will be transformed in the natural logarithmic scale. The model will include terms for sequence, period and product liking by the VAS-liking assessment. The effect of VAS-liking will be analyzed in different models with VAS-liking at T_1 (after 4 minutes), T_2 (after 10 minutes), and T_3 (after 15 minutes). The results of this analysis will be presented by product in terms of:

- The percentage of variance explained by product liking by the VAS-liking assessment.
- The standardized effect of product liking by the VAS-liking assessment on the endpoint, defined as the mean effect divided by the square root of its variance.

The ANCOVA analysis will be performed using the following SAS code:

```
PROC MIXED data=<> method=type3;  
By product;  
class subject sequence period;  
model log(PK parameter) = sequence period liking_score/ddfm=KR solution;  
run;
```

Another analysis of covariance (ANCOVA) will be conducted similarly to the above with the exception that it will be performed overall using mixed effects ANCOVA where the model will include, in addition, the subject as a categorical random effect to model the within subject correlations.

The same model will also be used to perform the analysis for human puffing topography parameters (total number of puffs, total puff volume, and total puff duration) to estimate the effect of VAS-liking score on the topography parameters.

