13.4 Statistical Outputs

Listing 15.4.1.1.1 Analysis SAS Output for Table 15.2.2.1.4

Listing 15.4.1.1.1.1 Analysis SAS Output for Table 15.2.2.1.4.1

Philip Morris Products S.A.
P4M3 Gen 2.0, P4-PK-04-US
[REDACTED] Statistical Analysis Plan Number CA34617

Listing 15.4.1.1.2 Analysis SAS Output for Table 15.2.2.1.5

Listing 15.4.1.1.2.1 Analysis SAS Output for Table 15.2.2.1.5.1

Listing 15.4.1.1.3 Analysis SAS Output for Table 15.2.2.2.4

Listing 15.4.1.1.4 Analysis SAS Output for Table 15.2.2.2.5

Listing 15.4.1.1.5 Analysis SAS Output for Table 15.2.2.2.6

Listing 15.4.1.1.6 Analysis SAS Output for Table 15.2.2.2.7

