Table 15.2.2.2.1 will have the following format, and Table 15.2.2.2.1.1 a similar format:

Table 15.2.2.2.1 Summary of Subscale Scores of ABOUT - Product Experience Questionnaire (PK Population)

Subscale	Statistics	Product		
		CA35	CM35	Cigarettes
P4M3 Gen 2.0				
Satisfaction	n	X	X	X
	Mean	X.X	X.X	X.X
	SD	X.XX	X.XX	X.XX
	CV%	X.X	X.X	X.X
	SEM	X.XX	X.XX	X.XX
	Minimum	XX	XX	XX
	Q1	X.X	X.X	X.X
	Median	X.X	X.X	X.X
	Q3	X.X	X.X	X.X
	Maximum	XX	XX	XX
	95% CI	XX-XX	XX-XX	XX-XX

CA35 = P4M3 Gen 2.0 Classic Auburn

CM35 = P4M3 Gen 2.0 Classic Menthol

SD = Standard deviation, CV% = Coefficient of variance, SEM = Standard error of mean, Q1 = 1st quartile, Q3 = 3rd quartile

CI = Confidence interval

PK Population = Subset of the safety population including all randomized subjects without major protocol deviations impacting the evaluability of the main objectives and for whom at least one nicotine PK parameter can be derived

Program: /CAXXXX/sas_prg/stsas/tab/ ADaM_program_name.sas DDMMYY YYYY HH:MM Status: DRAFT (Page X of Y)

Programmer Note: All subscales will be included in the summary table.

Philip Morris Products S.A.
P4M3 Gen 2.0, P4-PK-04-US

████████ Statistical Analysis Plan Number CA34617

Tables 15.2.2.2.2 and 15.2.2.2.3 will have the following format, and Tables 15.2.2.2.2.1 and 15.2.2.2.3.1 a similar format:

Table 15.2.2.2.2 Summary of VAS Craving Assessment (PK Population)

Scheduled Timepoint	Statistics	Product		
		CA35	CM35	Cigarettes
Pre-Product Use	n	X	X	X
	Mean	XX	XX	XX
	SD	X.XX	X.XX	X.XX
	CV%	XX	XX	XX
	SEM	X.XX	X.XX	X.XX
	Minimum	XX	XX	XX
	Q1	X.X	X.X	X.X
	Median	X.X	X.X	X.X
	Q3	X.X	X.X	X.X
	Maximum	XX	XX	XX
	95% CI	XX-XX	XX-XX	XX-XX

CA35 = P4M3 Gen 2.0 Classic Auburn

CM35 = P4M3 Gen 2.0 Classic Menthol

SD = Standard deviation, CV% = Coefficient of variance, SEM = Standard error of mean, Q1 = 1st quartile, Q3 = 3rd quartile

CI = Confidence interval

PK Population = Subset of the safety population including all randomized subjects without major protocol deviations impacting the evaluability of the main objectives and for whom at least one nicotine PK parameter can be derived

Program: /CAXXXX/sas_prg/stsas/tab/ ADaM_program_name.sas DDMMYYYY HH:MM Status: DRAFT (Page X of Y)

Programmer Note: All scheduled timepoints will be included in the summary table.

Philip Morris Products S.A.
P4M3 Gen 2.0, P4-PK-04-US

████████ Statistical Analysis Plan Number CA34617

Tables 15.2.2.2.4 through 15.2.2.2.7 will have the following format:

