Table 15.2.2.2.4 Inferential Analysis of VAS Liking Assessment on PK Parameters (PK Population)

Product	PK Parameter	Sum Square of Linking Score	Total Sum Square	Percentage*	Standardized Effect of Liking Score
CA35	XXXXX	XXXX	XXXX	XX.XX	XX
	XXXXX	XXXX	XXXX	XX.XX	XX
	XXXXX	XXXX	XXXX	XX.XX	XX
CM35	XXXXX	XXXX	XXXX	XX.XX	XX
	XXXXX	XXXX	XXXX	XX.XX	XX
	XXXXX	XXXX	XXXX	XX.XX	XX
Cigarettes	XXXXX	XXXX	XXXX	XX.XX	XX
	XXXXX	XXXX	XXXX	XX.XX	XX
	XXXXX	XXXX	XXXX	XX.XX	XX

CA35 = P4M3 Gen 2.0 Classic Auburn

CM35 = P4M3 Gen 2.0 Classic Menthol

PK Population = Subset of the safety population including all randomized subjects without major protocol deviations impacting the evaluability of the main objectives and for whom at least one nicotine PK parameter can be derived

Sum square of liking score and total sum square are from ANCOVA model.

*percentage = The percentage of variance explained by product liking by the VAS-liking assessment which calculated as Sum square of product liking score divided by total sum square and multiply 100.

Standardized effect of product liking is defined as the mean effect divided by the square root of its variance which is the t-value of the product liking score effect.

Program: /CAXXXXX/sas_prg/stsas/tab/ ADaM_program_name.sas DDMMYY YYYY HH:MM Status: DRAFT (Page X of Y)

Programmer Note: PK parameters (C_{max}, T_{max}, and AUC_{0-infinity}) and the human puffing topography parameters (total number of puffs, total puff volume, and total puff duration) to be included.

Philip Morris Products S.A.
P4M3 Gen 2.0, P4-PK-04-US

████████ Statistical Analysis Plan Number CA34617

Table 15.2.2.3.1 will have the following format:

Table 15.2.2.3.1 Summary of Human Puffing Topography Parameters (PK Population)

Topography Parameter	Statistics	Product	
		P4M3 Gen 2.0	
XXXXXXX	n	X	X
	Mean	X.X	X.X
	SD	X.XX	X.XX
	CV%	X.X	X.X
	SEM	X.XX	X.XX
	Minimum	XX	XX
	Q1	X.X	X.X
	Median	X.X	X.X
	Q3	X.X	X.X
	Maximum	XX	XX
	95% CI	XX-XX	XX-XX

CA35 = P4M3 Gen 2.0 Classic Auburn

CM35 = P4M3 Gen 2.0 Classic Menthol

PK Population = Subset of the safety population including all randomized subjects without major protocol deviations impacting the evaluability of the main objectives and for whom at least one nicotine PK parameter can be derived

SD = Standard deviation, CV% = Coefficient of variance, SEM = Standard error of mean, Q1 = 1st quartile, Q3 = 3rd quartile

CI = Confidence interval

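### The liking tables show a t-value under the heading of a standardized effect, and give no slope or confidence interval

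*SAP*

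**What the plan says.** SAP 7.3 (Inferential Analysis) and Protocol 12.7.2 name two results for the regression of PK parameters on VAS liking. The first is "The percentage of variance explained by product liking by the VAS-liking assessment". The second is a standardized effect of liking, "defined as the mean effect divided by the square root of its variance".

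The shell for Table 15.2.2.2.4 in SAP 14.4 has columns for the liking sum of squares, the total sum of squares, a percentage, and the standardized effect of the liking score. Its footnotes give the percentage as "calculated as Sum square of product liking score divided by total sum square and multiply 100" and explain the standardized effect as the quantity "which is the t-value of the product liking score effect". The layout is shared: "Tables 15.2.2.2.4 through 15.2.2.2.7 will have the following format". Tables 15.2.2.2.4 and 15.2.2.2.6 hold the by-product models for PK and topography. Tables 15.2.2.2.5 and 15.2.2.2.7 hold the corresponding overall models with subject as a random effect.

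The by-product code reads "model log(PK parameter) = sequence period liking_score/ddfm=KR solution". No code is shown for the overall model. SAP 13.4 plans SAS output listings for all four tables, beginning with "Listing 15.4.1.1.3 Analysis SAS Output for Table 15.2.2.2.4".

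**The concern.** An estimate divided by its standard error measures how far the estimate lies from zero in units of its own uncertainty. For a fixed association it rises roughly with the square root of the residual degrees of freedom, and it falls when records are missing. Headed as a standardized effect, it invites the reader to take it as the strength of the association.

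Two features of the plan make this matter. First, one heading covers models with quite different numbers of records and different error structures. Second, the exploratory objective is to describe associations, SAP section 2 states that no hypothesis is tested, and Protocol 12.1.5 marks a significance level as not applicable. A t-value answers a testing question that the study does not ask. Meanwhile the tables do not show how much Cmax, AUC or puff count changes per unit of liking, in what units, or how precisely that is known.

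**Working it through.** The plan gives no sample size, power or precision figure for this analysis, so there is no stated figure to reproduce. The check is how the tabulated quantity behaves when the association is held constant.

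**Inputs from the documents**
- 36 randomized subjects, three products, six sequences (SAP 3.1).
- By-product model: sequence, period and liking (SAP 7.3).
- Overall model: the same terms plus subject as a random effect (SAP 7.3).
- No topography is recorded during cigarette smoking (Protocol 7.8.2), so topography has at most 36 × 2 = 72 records overall. PK has at most 36 × 3 = 108.

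**Degrees of freedom, complete data**
- By product: within one product, period is determined by sequence, so sequence and period together have rank 6. Residual df = 36 − 6 − 1 = 29.
- Overall PK, within subject: 108 − 36 − 2 − 1 = 69.
- Overall topography, within subject: 72 − 36 − 2 − 1 = 33.

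The overall figures are the within-subject df that apply if subject is fitted as a fixed effect. Kenward-Roger df with a random subject effect will differ somewhat. SAP 7.3 lists no product term for the overall model.

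**Same association, different t**

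For partial correlation r, t = r × √df / √(1 − r²). With r = 0.3 (an assumed value), 0.3 / √0.91 = 0.3145.

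| Model | df | t | Ratio to by-product |
|---|---|---|---|
| By product | 29 | 0.3145 × √29 = 1.69 | 1 |
| Overall, PK | 69 | 0.3145 × √69 = 2.61 | √(69/29) = 1.54 |
| Overall, topography | 33 | 0.3145 × √33 = 1.81 | √(33/29) = 1.07 |

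The ratios do not depend on r.

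**Same slope, illustrative simulation**

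Assumptions: slope 0.30 on a liking score with SD 1, total residual variance 1 and, for the overall model, within-subject correlation 0.8. Subject was fitted as fixed effects in the overall model and period was left out. There were 1,000 replicates for each by-product size and 1,500 for the overall model.

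| Model | Mean slope | Mean t | Mean % of variance |
|---|---|---|---|
| By product, N = 36 | 0.30 | 1.71 | 9.6 |
| By product, N = 72 | 0.30 | 2.43 | 8.7 |
| By product, N = 144 | 0.30 | 3.53 | 8.5 |
| By product, N = 288 | 0.30 | 4.98 | 8.2 |
| Overall, 36 × 3 | 0.30 | 5.75 | 6.0 |

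With the slope unchanged, t roughly doubles when N goes from 36 to 144 (3.53 / 1.71 = 2.06), while the percentage drifts down slightly. In the overall model t is 5.75 / 1.71 = 3.4 times the by-product value, because there are more records and because between-subject variance is removed. So the size of the by-product to overall gap depends on what is held constant and on the assumed correlation.

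**The case against.** The strongest reply is that the plan already reports an effect size and is open about the t-value. Most of this stands.

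- **A reader might infer that no effect size is reported.** That is wrong. The percentage of variance explained is a column in the same shell and the first result named in SAP 7.3 and Protocol 12.7.2. What remains is that it has no sign, and that its denominator and model differ between by-product and overall analyses (9.6% against 6.0% for one slope in the simulation).
- **A reader might infer that associations cannot be compared at all.** The problem is confined to the t column, across by-product and overall models. The three by-product values come from the same crossover subjects with near-equal N and are roughly comparable with one another. SAP 7.3 presents the two analyses separately and plans no formal comparison of them.
- **The footnote discloses that the column is a t-value.** True, so a careful reader is not deceived. The heading still says something else, and the shell has no df column from which to convert t to a partial correlation.
- **The slope will be in the SAS output listings.** For the displayed by-product code, yes, with its standard error. A reader might infer that the confidence interval is produced too. The model statement requests the solution but not CL, so PROC MIXED will not print confidence limits. Output options for the overall model are not specified.
- **Stakes are low.** The analysis is exploratory, and SAP section 14 says shells may change. This bears on priority, not on whether the label is right.

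**Conclusion.** The narrow point holds. The column headed as a standardized effect is a t-value by the SAP's own definition. It is not an effect size and should not be read across by-product and overall tables. No signed estimate in interpretable units, and no interval, is tabulated.

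At an equal partial correlation the inflation from by-product to overall is about 1.5-fold for PK and about 1.07-fold for topography. These figures assume complete data and within-subject df. A reader might infer that the same association looks almost twice as large overall: taking df of about 100 for 108 records gives t = 3.14 against 1.69. The documents do not support that figure, because it ignores the subject effect that defines the overall model, and topography cannot exceed 72 records. The larger gap in the simulation rests on an assumed slope and correlation and is illustrative only.

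The main PK results are untouched. This is a minor reporting improvement.

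**What to change.** 1. Rename the column t-value in the shell for Tables 15.2.2.2.4 to 15.2.2.2.7, and align the wording in SAP 7.3.
2. Add the liking slope b with its 95% CI, for example per 10 mm of VAS. For log-scale PK parameters, back-transform the estimate and both limits as 100 × (exp(10b) − 1), so the table reads as % change per 10 mm.
3. Add the CL option to the by-product model statement. Write out the overall model code and request the same solution and limits there.
4. If a standardized effect is wanted, report the slope per SD of liking, and state which SD is used in the by-product and overall models.
5. Keep the percentage of variance explained.
6. Record the change from Protocol 12.7.2 in SAP section 11.

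The cost is a shell edit, a few lines of SAP text and one SAS option. No new data and no new model are needed.
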